6.10.3. Assessing Relationship to Study Treatment

The Investigator will categorize each AE as to its potential relationship to study drug: **unrelated, unlikely related, possibly related, probably related** and **definitely related**. Items to be considered when assessing the relationship of an AE to the study treatment are as follows:

- Temporal relationship of the onset of the event to the initiation of the study treatment
- The course of the event, considering especially the effect of discontinuation of study treatment or reintroduction of study treatment, as applicable
- Whether the event is known to be associated with the study treatment or with other similar treatments
- The presence of risk factors in the study subject known to increase the occurrence of the event
- The presence of non-study treatment-related factors that are known to be associated with the occurrence of the event

The relationship categories of unrelated and unlikely related will be summarized for reporting purposes as **Not Related**. For Not Related events, the time course between the administration of study drug and the occurrence or worsening of the AE rules out a causal relationship with study drug, and another cause of the AE (concomitant drugs, therapies, complications, etc.) is suspected.

The relationship categories of possibly, probably and definitely related will be summarized for reporting purposes as **Related**. Only AEs thought to be caused by the study drug should be classified as “related to study drug.” For Related events, the time course between the administration of study drug and the occurrence or worsening of the AE is consistent with a causal relationship, and no other cause (concomitant drugs, therapies, complications, etc.) can be identified. The definition implies a reasonable possibility of a causal relationship between the event and the study drug. This means that there are facts (evidence) or arguments to suggest a causal relationship.

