7.7 Evaluation of Safety Endpoints

All safety variables will be evaluated for the safety population (SP). The analyses of treatment-emergent adverse events (TEAEs) will be performed overall and for subjects enrolled under global

amendment 1 and global amendment 2 separately. The analysis on the SOC and PT level will be repeated for the All Screened population to cover all AEs, also those recorded prior to first treatment with the study drug.

Treatment-emergent adverse events (TEAEs) will be summarized overall and by causal relationship and severity. TEAEs will be coded using the latest MedDRA version at the time of database close. Incidences and percentages will be provided on the subject-level (n), overall as well as on the system organ class (SOC) level and on the preferred term (PT) level for all subjects and by nevanimibe dose category. Results will additionally be prepared by time range. The suitable time ranges will be selected during the DRM for Cohort 1. A subject with more than one AE overall or assigned to one SOC or assigned to one PT will be counted once for the worst category (causal relationship or severity) on the subject level. For the summarization by relationship to study drug, the relationship will be categorized as “related” and “not related,” where related AEs are those with at least a possible relationship to the study treatment. For the summarization by nevanimibe dose, subjects with more than one AE overall or assigned to one SOC or assigned to one PT will be counted once on the subject level at the lowest nevanimibe dose category on which they experience the AE (i.e., a subject with two AEs, one when treated with 1000 mg BID and one when treated with 1500 mg BID, will be counted once at the 1000 mg BID dose). Additionally, the number of AEs per patient-year of treatment will be calculated by nevanimibe dose as (sum of number of AEs of subjects at the respective nevanimibe dose) / (patient-years of treatment at the respective nevanimibe dose).

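### Protocol 6.10.3 leaves two of four kinds of adverse event in neither the Related nor the Not Related class, and its no-other-cause condition contradicts the possible-relationship standard used there and in SAP 7.7

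*Protocol*

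**What the plan says.** Protocol 6.10.3 asks the investigator to rate each adverse event on five levels, from unrelated to definitely related, after weighing a short list of considerations. One of these is whether non-treatment factors could account for the event. The five levels are not defined individually. They are collapsed into two reporting classes, and only the classes are defined:

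- Not Related (unrelated, unlikely related): the time course "rules out a causal relationship with study drug, and another cause of the AE (concomitant drugs, therapies, complications, etc.) is suspected".
- Related (possibly, probably, definitely related): the time course fits a causal relationship, and "no other cause (concomitant drugs, therapies, complications, etc.) can be identified".

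The mapping sentence begins "The relationship categories of possibly, probably and definitely related will be summarized for reporting purposes as" and names Related as the class. Two further sentences in the paragraph on Related pull in different directions. One is restrictive: "Only AEs thought to be caused by the study drug should be classified as" related. The other is looser: "The definition implies a reasonable possibility of a causal relationship between the event and the study drug".

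SAP 7.7 uses the looser standard for the tables: "related AEs are those with at least a possible relationship to the study treatment". It sets no condition about other causes.

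**The concern.** The only operational text a site has for the two classes joins two conditions with *and* in each case, so the classes are not complements of each other. The case most likely to need judgement, plausible timing with another possible explanation, has no class. *Possibly related* normally describes just that situation, yet it maps to a class whose definition excludes it.

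This matters more here than in a controlled trial. The study is open-label with no reference therapy (Protocol 5.3.6 and synopsis), so no comparator shows the background event rate, and investigator attribution is one of the few tools for separating drug effects from background. Alternative causes can readily be named. All subjects take chronic glucocorticoids (Protocol 4.2, 5.7). Nevanimibe is described as a moderate CYP3A4 inhibitor (Protocol 5.8), and Appendix 5 lists hydrocortisone and dexamethasone as substrates. An event arising from that interaction would have an identifiable concomitant-drug cause and would fail the Related definition, even if nevanimibe contributed.

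The outputs at stake are SAP tables 14.3.1.5 and 14.3.1.6 (related TEAEs), the optional time-to-first-related-TEAE curve in SAP 7.7, and the duty in Protocol 6.10.1 and 6.10.4.2 to report related serious events however long after study completion.

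**Working it through.** The plan gives no figure to reproduce. The check is a truth table built from the two definitions in Protocol 6.10.3, crossing timing with other cause.

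| Timing | Other cause | Meets Related? | Meets Not Related? | Class |
|---|---|---|---|---|
| Consistent | None identified | Yes | No | Related |
| Consistent | Identified | No (other-cause condition fails) | No (timing condition fails) | None |
| Ruled out | Suspected | No | Yes | Not Related |
| Ruled out | None suspected | No (timing condition fails) | No (other-cause condition fails) | None |

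Two of the four rows have no class.

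Next, compare the standards for Related.

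1. The class definition needs consistent timing and no other identifiable cause.
2. The later sentence in the same paragraph needs only a reasonable possibility.
3. SAP 7.7 needs at least a possible relationship.

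Standard 1 adds a condition that 2 and 3 do not have. An event in row 2 can satisfy 2 and 3 but cannot satisfy 1. Adding a condition can only shrink the class, so any error from this clause runs towards fewer Related events.

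Size. Let *p* be the share of events meeting the reasonable-possibility standard that also have another identifiable cause. Let *s* be the share of those that investigators rate unrelated or unlikely because of the clause.

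- Proportion lost from Related = *p* × *s*.
- If investigators still rate these events possibly related, *s* = 0 and the loss is 0.
- If they apply the clause strictly every time, *s* = 1 and the loss is *p*.

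The documents give neither *p* nor *s*, and no adverse-event rates for this trial. The loss therefore lies between zero and *p*, with *p* unknown. A numerical illustration would only return its own assumptions.

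What depends on the rating and what does not:

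- Dependent: tables 14.3.1.5 and 14.3.1.6, any time-to-first-related-TEAE display, and reporting of related serious events after study completion.
- Not dependent: all-causality TEAE tables by dose (14.3.1.1 to 14.3.1.4), and collection of serious events within the window, which Protocol 6.10.4.2 requires whatever the causality rating.

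**The case against.** The strongest reply is that the two-class text serves reporting only. The investigator's task is the five-level rating, and there other causes are one consideration among several, not a veto. Another consideration is whether the event is known to occur with the treatment, which favours relatedness for recognised effects. Both the protocol mapping and SAP 7.7 count *possibly related* as Related, so an investigator who ticks that level gets the event counted. This stands, and it is why under-counting cannot be treated as certain. It does not remove the conflict: the five levels have no definitions of their own, so the class text is the only definition available to a site.

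A second reply is that relatedness is secondary. The safety endpoints in Protocol 9.6.1 rest on incidence; there are no safety targets and no safety inference. All-causality tables by dose keep toxicity visible. The safety meeting in Protocol 3.5 is triggered by the event itself, and the sponsor and medical monitor then judge relatedness. The figure listed in SAP Appendix 1 is time to first TEAE, not first related TEAE. All of this stands and limits the consequences.

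Some stronger readings are tempting but unsupported:

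- A reader might infer that the rule sends plausibly timed events to Not Related. It does not: that class requires that "the time course between the administration of study drug and the occurrence or worsening of the AE rules out a causal relationship with study drug", which these events also fail.
- A reader might take Related to require that no other cause exists. The text requires only that none can be identified.
- A reader might assume that another cause is nearly always present in this population. The documents give no figure for this. Steroid regimens must be stable for at least 4 weeks before enrollment (Protocol 4.2) and are expected to stay unchanged on treatment (Protocol 3.3), so Cohort 2 reductions are not concurrent with dosing.

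**Conclusion.** The definitions are not exhaustive, and the no-other-cause condition contradicts the rest of its own section and SAP 7.7. That follows from the wording alone and needs no assumption. The consequence is conditional: if sites apply the condition literally, related events may be under-counted, and if sites differ in how they read it, they will be classified inconsistently. The direction of any error from this clause is known; its size is not, and it may be zero. The statement that drug-related events will be under-counted goes further than the documents allow. Overall TEAE incidence and in-window serious-event collection are unaffected. The point merits correction because attribution carries weight in an uncontrolled trial and the repair is small.

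**What to change.** In Protocol 6.10.3, delete the requirement that "no other cause (concomitant drugs, therapies, complications, etc.) can be identified" and replace the two class definitions with a complementary pair:

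- Related (possibly, probably, definitely): there is a reasonable possibility that study drug caused or contributed to the event, even if another cause is also possible.
- Not Related (unrelated, unlikely): there is no such reasonable possibility.

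Because the second is the negation of the first, every event has exactly one class. Timing and other causes remain considerations in the investigator's judgement. Bring the sentence restricting Related to events thought to be caused by the drug into line with this. SAP 7.7 already agrees and should stay as it is.

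The cost is about two sentences in an amendment, with a note to sites. If ratings already entered are re-checked, the workload covers a planned 20-24 evaluable subjects. Do it before database lock, and keep the original ratings in the audit trail that Protocol 10.7 provides. There are two downsides: the reported related-event rate may rise, and a re-check is retrospective reclassification by unblinded investigators, which should be disclosed in the study report.

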6.10.4. Serious Adverse Events

6.10.4.1. Definition of Serious Adverse Event

A serious adverse event (SAE) is any untoward medical occurrence that:

- Results in death
- Is life-threatening (Note: The term “life-threatening” in the definition of “serious” refers to an event in which, in view of either the Investigator or Sponsor, the subject was at immediate risk of death at the time of the event; it does not refer to an event that hypothetically might have caused death if it were more severe.)
- Requires inpatient hospitalization or prolongation of an existing hospitalization

Notes:

Any hospital admission with at least one overnight stay will be considered an inpatient hospitalization. An emergency room visit without hospital admission will not be recorded as an SAE under this criterion, nor will hospitalization for a procedure scheduled or planned before signing of informed consent. However, unexpected complications and/or prolongation of hospitalizations that occur during elective surgery should be recorded as AEs and assessed for seriousness.

The following hospitalizations are not considered to be SAEs because there is no AE (i.e., no untoward medical occurrence) associated with the hospitalization:

- Hospitalizations for respite/hospice care
- Hospitalization planned prior to informed consent (where the condition requiring the hospitalization has not changed post study drug administration)
- Results in persistent or significant incapacity or substantial disruption of the ability to conduct normal life functions
- Is a congenital anomaly/birth defect, or
- Is determined to be an important medical event (at the discretion of the Investigator)

Note: Important medical events that may not result in death, be life-threatening, or require hospitalization may be considered serious when, based upon appropriate medical judgment, they may jeopardize the subject and may require medical or surgical intervention to prevent one of the other outcomes listed in the SAE definition. Examples of such medical events include allergic bronchospasm requiring intensive treatment in an emergency room or at home, blood dyscrasias or convulsions that do not result in inpatient hospitalization, or the development of drug dependency or drug abuse.

6.10.4.2. Reporting SAEs – Procedure for Investigators

Initial Reports

Adverse events and all information regarding SAEs, whether reported by the subject or observed by the investigator/study personnel, must be documented in the subject's medical record and reported by recording all pertinent information on the eCRF AE/SAE Forms in the electronic data capture (EDC) system.

SAEs, regardless of causality assessment, must be collected beginning from the time the subject signs the informed consent form until the last study visit or 30 days after the last dose of study drug, whichever is longer. All SAEs must be reported within the EDC system by the study site. Study site personnel should complete the eCRF AE/SAE Form in the EDC system and the investigator should assess the causality **within 24 hours** of knowledge of the event (this refers to any AE that meets any of the aforementioned seriousness criteria). Via the EDC system, Clinical Safety will receive the report in parallel via email at [contact]. Any SAE judged by the Investigator to be related to the study treatment should be reported to the Sponsor regardless of the length of time that has passed since study completion.

The minimum information required for the initial SAE report is covered by the eCRF AE/SAE Form. If requested by Clinical Safety, SAE reports should be followed as soon as possible by detailed descriptions including copies of hospital case reports, autopsy reports and other documents (see Follow-up Reports, below).

Clinical Safety contact information for this study is as follows:

- If the EDC system is unavailable, the SAE will be reported via telephone at [contact]
- For urgent safety issues, call the Medical Monitor at [contact]

Follow-up Reports

All AEs and SAEs must be followed to resolution or, if resolution is unlikely, to stabilization.

Within 24 hours of receipt of follow-up information, the Investigator must update the eCRF AE/SAE Form within the EDC system. Any requested supporting documentation (e.g., subject discharge summary or autopsy reports) should be submitted to Clinical Safety via e-mail at [contact] or fax at [contact]. All personal data must be redacted prior to submission; instead, please provide the study number (Millendo ATR-101-202) and the subject ID on each document. If the follow-up information changes the Investigator's assessment of causality, this should also be noted in the follow-up section within the eCRF AE/SAE form.

The Investigator should notify the IRB/EC of the occurrence of the SAE, in writing, in accordance with local requirements. A copy of this communication must be filed in the Investigator's files for this study.

6.10.5. Pregnancy Reporting

Any pregnancy that occurs following study drug dosing where the estimated date of conception occurred either prior to the study termination visit or within 30 days of last study treatment must be reported. The Investigator should report the pregnancy using the Pregnancy Form within the EDC system within 24 hours of being notified. Via the EDC system, Clinical Safety will receive the report in parallel via email at [contact]. **The contact information for reporting pregnancies is the same as for reporting SAEs (Section 6.10.4.2).**

A subject becoming pregnant while on study drug will immediately be withdrawn from the study and early termination (ET) study procedures will be performed.

The subject should be followed by the Investigator until completion of the pregnancy. If the pregnancy ends for any reason before the anticipated date, the Investigator should notify Clinical Safety as specified in the Safety Manual. At the completion of the pregnancy, the Investigator will document the outcome of the pregnancy. If the fetus has a congenital anomaly, the Investigator should follow the procedures for reporting an SAE.

6.10.6. Regulatory Reporting of Adverse Events

AEs will be reported to the regulatory authorities in compliance with local and regional law and established guidance by the Sponsor or by a third party acting on behalf of the Sponsor. The format of these reports will be dictated by the local and regional requirements.

6.11. Laboratory Tests

Blood, saliva, and urine samples for assessments of clinical laboratory parameters and/or PK will be obtained as shown in the study schedule in [Appendix 1](#). For each study visit, the first hormone sample collection that is obtained at the study site should be done between 6-10 AM (06:00-10:00), as close to 8 AM (08:00) as practicable. Additionally, at study visits, blood and corresponding saliva samples will be obtained at approximately the same time (± 15 minutes) to facilitate correlation of results.

On days that saliva samples are collected, the timing of glucocorticoid doses, mineralocorticoid doses (if applicable), nevanimibe HCl doses (if applicable), and saliva sample collections should be kept consistent as much as possible per subject. For salivary profiles collected on Days -8, 22, 50, 78, and 106, samples should be obtained at approximately 8 AM (08:00), noon (12:00), 4 PM (16:00), 8 PM (20:00), and 10-11 PM (22:00-23:00). At Visits T1, T2, T3, and T4, samples will be collected at the study site at approximately 8 AM (08:00), 10 AM (10:00), and noon (12:00).

The 8 AM (8:00) sample should be collected prior to the subjects' morning dose of glucocorticoid and mineralocorticoid (if applicable) and will also be assessed for P (in premenopausal women only) and cortisol. The timing of the 8 AM (08:00), 10 AM (10:00), noon (12:00) samples should be adjusted to correspond to just before (within 30 minutes before), 2 hours after, and 4 hours after (respectively) administration of the morning glucocorticoid, mineralocorticoid (if applicable) and/or study drug (if applicable) doses. In general, the samples should be collected prior to relevant glucocorticoid and mineralocorticoid (if applicable) doses if possible.

6.11.1. Clinical Laboratory Assessments

Testing of clinical laboratory samples will be carried out by the central clinical laboratory using validated methods and will include the tests listed in [Table 3](#). In addition, stored serum and plasma samples may be assayed for parameters relevant to hormone metabolism (no DNA samples will be stored). Total blood volumes to be collected will be provided in the Laboratory Manual. Abnormal, clinically significant results may be verified to rule out laboratory error. Persistent relevant abnormal values must be followed up until the cause is determined or until they return to the baseline value. Abnormal laboratory findings that are considered clinically significant by the Investigator should be recorded as AEs as appropriate ([Section 6.10](#)).

Table 3: List of Clinical Laboratory Tests

Hematology	hematocrit (Hct), hemoglobin (Hgb), platelet count, red blood cell (RBC) count, white blood cell (WBC) count with differential
Chemistry	albumin, alkaline phosphatase, alanine aminotransferase (ALT; SGPT), aspartate aminotransferase (AST; SGOT), blood urea nitrogen (BUN), calcium, creatinine, glucose, total bilirubin, total protein, electrolytes (magnesium, sodium, potassium, chloride, bicarbonate)
Coagulation	PT, aPTT, INR
Plasma or Serum Hormones	17-hydroxyprogesterone, androstenedione, adrenocorticotrophic hormone, cortisol, progesterone, total testosterone, and 11-ketotestosterone
Salivary Hormones	17-hydroxyprogesterone, progesterone (premenopausal women “08:00” sample only), and cortisol (“08:00” sample only)
Urinalysis	appearance, bilirubin, color, glucose, ketones, leukocyte esterase, nitrite, occult blood, pH, protein, specific gravity, urobilinogen; microscopic examination will be performed if leukocyte esterase, nitrite, and/or occult blood are positive
Other	HBsAg, HCV, HIV, urine drug screen

aPTT, activated partial thromboplastic time; HBsAg, hepatitis B surface antigen; HCV, hepatitis C virus; HIV, human immunodeficiency virus; INR, international normalized ratio; PT, prothrombin time

6.11.2. Pharmacokinetic Assessments

Testing of PK samples will be carried out by the central PK laboratory using validated methods. Logistic considerations may dictate a deviation from the specified time point; therefore, a window is permitted around each sampling time point, as shown in [Table 4](#): sampling times up to and including 1 hour postdose have a window of ± 5 min and subsequent time points have a window of ± 10 min. At Treatment Period visits, study drug and replacement glucocorticoid and mineralocorticoid (if applicable) doses are expected to be administered at approximately the same time. At Treatment Period visits, actual dosing times of nevanimibe HCl, glucocorticoids, and mineralocorticoids (if applicable) must be recorded using the eDiary; and actual times of PK sampling must be recorded on the eCRF.

Table 4: Pharmacokinetic Sampling Time Points

Visit	Sampling Time Points (Morning Dose Only)
T1, T2, T3, T4, T5/EoT	0 hours (trough, within 30 min predose); and 1 hour (± 5 min), 2 hours (± 10 min), 3 hours (± 10 min) and 4 hours (± 10 min) postdose

Specific collection and shipment procedures for PK samples are provided in the Laboratory Manual.

PK parameters will be computed using non-compartmental methods. The PK parameters outlined in Table 5 will be estimated for nevanimibe and its major metabolite(s) as data permit and as appropriate. PK parameters may also be estimated for replacement glucocorticoids and/or mineralocorticoids as appropriate.

Table 5: Pharmacokinetic Parameters

C_{last}	last quantifiable drug concentration determined directly from individual concentration-time data
C_{max}	maximum observed drug concentration determined directly from individual concentration-time data
C_{max}/D	dose-normalized C_{max} , calculated as the ratio of C_{max} to dose
T_{max}	observed time to reach maximum drug concentration
AUC_{0-4}	area under the concentration-time curve from time zero to 4 h after dosing, calculated using the linear-up/log-down trapezoidal rule
AUC_{0-4}/D	dose-normalized AUC_{0-4} , calculated as the ratio of AUC_{0-4} to dose
AUC_{0-t}	area under the concentration-time curve from time zero to the time of the last quantified concentration, calculated using the linear-up/log-down trapezoidal rule
λ_z	terminal phase rate constant, estimated by linear regression through the terminal phase of the log concentration-time profile
$t_{1/2}$	terminal phase half-life, calculated as: $t_{1/2} = \frac{\ln(2)}{\lambda_z}$
$AUC_{0-\infty}$	area under the concentration-time curve from time zero to infinity (first dose only), calculated as $AUC_{0-4} + C_{last}/\lambda_z$
$AUC_{\%extrap}$	percentage of $AUC_{0-\infty}$ extrapolated, represented as $(1 - AUC_{0-t}/AUC_{0-\infty}) \times 100$
CL/F	oral clearance calculated as: dose/ $AUC_{0-\infty}$ (Day 1 only)

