The dose rationale is further supported by the 13-week dog toxicity study with $AUC_{0-24\text{ hr}}$ margins relative to the dog No Observed Adverse Effect Level (NOAEL) of 2.0 to 8.0 for the highest (2000 mg BID) and lowest (500 mg BID) nevanimibe HCl doses planned, respectively.

Acceptably managed classic CAH patients generally have mildly elevated, rather than completely normal, 17-OHP levels (Speiser, 2010). Thus, the overall goal of the study is to show clinically meaningful decreases in 17-OHP that are aligned with clinical practice goals. Two classic CAH patient populations have been identified: those with serum 17-OHP $\geq 4x$ ULN (Cohort 1) and those with serum 17-OHP $< 4x$ ULN (Cohort 2) at screening. The vast majority of subjects are expected to be on suppressive (supra-physiologic) glucocorticoid doses at screening, but it is possible that potential subjects may have an elevated 17-OHP while on less than supra-physiologic glucocorticoid doses.

The study design and dose levels are appropriately supported by existing clinical and nonclinical data.

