7.8 Evaluation of Pharmacokinetic Variables

Pharmacokinetic parameters (C_{last} , C_{max} , C_{max}/D , T_{max} , AUC_{0-4} , AUC_{0-4}/D , AUC_{0-t} , λ_z , $t_{1/2}$, $AUC_{0-\infty}$, $AUC_{\%extrap}$, CL/F) for nevanimibe and its major metabolite(s) will be computed as data permit and as appropriate

using non-compartmental methods employing WinNonlin® Phoenix version 6.3 or later (Pharsight Corp., Mountain View, CA). PK parameters may also be estimated for replacement glucocorticoids and/or mineralocorticoids as appropriate.

The pharmacokinetic analyses will be described in detail in a separate PK Analysis Plan by Certara USA, Inc. (Princeton, New Jersey, USA) as it will be conducted separately from the analyses described in this document.

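### Half-life, AUC0-inf and Day 1 CL/F rest on profiles that stop at 4 h; unless elimination and absorption are fast, the end-of-treatment trough supports a better clearance estimate with no new samples

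*Protocol*

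**What the plan says.** Protocol 6.11.2, Table 4, sets the same sampling at T1 to T5. There is a predose sample, "0 hours (trough, within 30 min predose"), then samples at 1 and 2 h, and finally "3 hours (± 10 min) and 4 hours (± 10 min) postdose". Doses are taken about 12 hours apart with food (Protocol 5.3.1).

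Table 5 then defines:
- lambda-z as the "terminal phase rate constant, estimated by linear regression through the terminal phase of the log concentration-time profile", with half-life as ln(2)/lambda-z. Neither is tied to a visit.
- AUC0-inf as the "area under the concentration-time curve from time zero to infinity (first dose only), calculated as" AUC0-4 + Clast/lambda-z.
- CL/F as "oral clearance calculated as: dose" divided by AUC0-inf, on Day 1 only.
- AUC%extrap, with no threshold and no stated use.

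SAP 7.8 repeats the list. It says the parameters "for nevanimibe and its major metabolite(s) will be computed as data permit and as appropriate" and leaves the detail to a separate PK Analysis Plan, which is not among the documents. Protocol 9.7.2 adds that parameters are computed only as far as the collection times allow, and names Cmax, Tmax, AUC0-4 and trough as the assessments. No exposure over the 12-hour dosing interval is listed. Determining the PK parameters is a secondary objective (Protocol 2.2).

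**The concern.** AUC0-inf and CL/F depend on the unsampled tail. If that tail is most of the area, they are governed by a slope fitted to two or three points near the peak. Such a slope can be absent, or can reflect absorption or distribution more than elimination. The wording about data permitting does not say when a value is too poor to report. AUC0-4, the one area the schedule measures directly, covers only the first third of the dosing interval.

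At end of treatment the trial already draws what it needs for a full interval. No titration step is listed at T5, and the last scheduled titration call comes before Day 99 (Protocol 7.3.8, 7.3.9). The T5 trough and the T5 postdose samples therefore normally belong to one unchanged dose. At T2 they do not, because every subject is up-titrated that morning. The plan collects the T5 trough but does not use it to complete the interval.

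**Working it through.** **Inputs from the documents.** Sampling at 0, 1, 2, 3 and 4 h; the Table 5 formulas; a 12 h interval; stated AUC0-24 margins to the dog NOAEL of 2.0 (2000 mg BID) and 8.0 (500 mg BID) in Protocol 3.2.

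**Assumed, because the documents do not give them.** One-compartment oral model, half-life 1 to 12 h, ka 0.5, 1 or 2 per h; for the noise runs, true Tmax 1 or 2 h and 15% log-scale error.

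**The plan's own figure.** 8.0/(2000/500) = 2.0, so the two margins agree under dose proportionality. They cannot be rebuilt, since neither the dog nor the human AUC is given.

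**Step 1, points available.** Points after the observed Cmax number three if it falls at 1 h, two at 2 h and one at 3 h (no slope).

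**Step 2, area beyond 4 h.** With k = ln(2)/half-life, the share is (ka·e^(−4k) − k·e^(−4ka))/(ka − k). For half-life 4 h and ka 1, k = 0.1733 and the share is (0.500 − 0.1733 × 0.0183)/0.8267 = 0.60.

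| Half-life (h) | AUC0-inf beyond 4 h | Points after Cmax (ka 0.5 / 1 / 2) | AUC0-12 recovered (Step 5) |
|---|---|---|---|
| 1 | 10–32% | 2 / 3 / 3 | 0.88–0.94 |
| 2 | 30–51% | 2 / 2 / 3 | 0.94–0.96 |
| 4 | 55–69% | 1 / 2 / 3 | 0.96–0.98 |
| 8 | 74–83% | 0 / 1 / 2 | 0.98–0.99 |
| 12 | 82–88% | 0 / 1 / 2 | 0.98–0.99 |

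**Step 3, Day 1 clearance, noise-free example (half-life 4 h, ka 1, dose/V = 1).**
- Concentrations at 1 to 4 h: 0.572, 0.692, 0.659, 0.583. AUC0-4 by linear-up/log-down is 2.213.
- The two post-peak points give lambda-z = ln(0.659/0.583) = 0.123.
- AUC0-inf = 2.213 + 0.583/0.123 = 6.95, against a true 1/k = 5.77. CL/F is 5.77/6.95 = 0.83 of the truth.

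**Step 4, with 15% noise (5th to 95th percentile, Tmax 1 h).**
- True half-life 1 h: estimate 0.9–1.8 h, AUC0-inf 0.82–1.08 of true, slope always obtained.
- True half-life 4 h: estimate 1.8–22 h, AUC0-inf 0.63–3.7 of true, no slope in 16% of profiles.
- True half-life 8 h: estimate 2.1–52 h, AUC0-inf 0.42–5.4 of true, no slope in 41%.
- With Tmax 2 h and half-life 2–12 h, 45–69% of profiles give no slope.

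In a two-compartment case (half-lives 1 and 10 h, no noise) the estimated terminal half-life is 2.0–3.8 h. AUC0-inf is 0.55–0.58 of true, so CL/F is 1.7–1.8 times too high.

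**Step 5, the alternative.** AUC0-12 = AUC0-4 at steady state + 8 × (C4 − C12)/ln(C4/C12), with C12 set to the predose value. In the Step 3 example at steady state, AUC0-4 = 2.713, C4 = 0.669 and C12 = 0.173. The second term is 8 × 0.496/1.354 = 2.93. The total of 5.64 is 0.98 of the true 5.77.

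With 15% noise, the 5th to 95th percentile range stays within about 0.80 to 1.13 in every one-compartment case run. The noise-free two-compartment case gives 1.00–1.01. AUC0-4 alone is 35–71% of AUC0-12 for half-lives of 2 to 12 h.

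**The case against.** Five points deserve weight.

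- **A reader might infer that 4 h of sampling cannot support these parameters at all.** The documents do not support that, because they give no half-life or Tmax. At a 1 h half-life, a noise-free fit through 2, 3 and 4 h gives CL/F of 0.84 to 1.14 of the truth.
- **The error can be overstated.** The same mechanical fit over half-lives of 2 to 12 h gives CL/F as low as 0.18 of the truth. That case includes a pre-peak point, which Table 5 would not call terminal phase. Its AUC%extrap is 96%, so the problem would be visible. The 0.18 should not be quoted as the size of the problem.
- **The plan is hedged.** The parameters are conditional, and the named PK assessments (Cmax, Tmax, AUC0-4, trough) are all measurable. The unseen PK Analysis Plan may contain acceptance rules. This softens the point, but the protocol and SAP set no limit and fix the CL/F formula to Day 1.
- **A reader might also infer that the trial fails in a duty to verify the dog-NOAEL margin.** No objective asks for that. The margin is design rationale, and the higher doses are also supported there by the adrenocortical carcinoma study.
- **The alternative has weaknesses of its own.** It bridges an unsampled gap from 4 to 12 h. It also mainly covers each subject's final dose, which titration selects by response, so exposure by dose is not a clean comparison. This stands and should be stated with the results.

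**Conclusion.** The point holds in conditional form. Unless half-life is about 1 h and absorption is fast, much or most of AUC0-inf would be extrapolated from at most three post-peak points, and half-life and Day 1 CL/F would be imprecise, biased or unobtainable. For lambda-z and half-life the 4 h limit applies at every visit, since Table 5 does not restrict them to Day 1.

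The sizes rest on assumed kinetics and noise and should be rechecked against the sponsor's earlier data. The consequence is limited to secondary, descriptive pharmacokinetics; the primary endpoint is untouched. It is still worth acting on, because a better clearance estimate is available from samples already planned.

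**What to change.** In Table 5, SAP 7.8 and the PK Analysis Plan:

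1. At end of treatment (T5, or T4 for subjects treated under amendment 1), compute steady-state AUC0-12 from the 0–4 h samples plus the predose value placed at 12 h, log-linear from 4 to 12 h. Report CL/F as dose/AUC0-12. Use other visits only where the dose was unchanged at the visit and for long enough before it. Exclude visits after a recent drug holiday, down-titration or stop.
2. Use the actual evening-dose time. It is in the eDiary, which SAP 7.9 currently only lists, so it must become an analysis input.
3. Report lambda-z, half-life, AUC0-inf and Day 1 CL/F only when a pre-stated rule is met, for example at least three points after Cmax and AUC%extrap of 20% or less. Otherwise list them as not estimable. If half-life is 2 h or longer, expect this rule to withhold most values; that is its purpose.
4. Align the formulas: AUC0-inf is built on AUC0-4 but AUC%extrap on AUC0-t. They agree only when the last quantifiable sample is at 4 h.
5. Optionally, show 2 × AUC0-12 by dose, descriptively, beside the sponsor's NOAEL AUC0-24, which the documents do not give.

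The cost is wording and programming, with no extra blood draw. State the assumptions with the results: steady state, a gap of roughly 12 hours, log-linear decline from 4 to 12 h and, for item 5, equal morning and evening exposure.
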